11.5 Errors

- 11.5.1 If the meter reports an error code during blood glucose testing, the instructions shown in the UG should be followed. Re-testing is recommended (per the UG). The reason for the repeated test will be documented in the comments section of the form. No more than a total of 3 attempts are allowed.
- 11.5.2 The study staff will record all meter error codes as appropriate for the meter tests as it occurs.

11.6 Hematocrit

- 11.6.1 At least one hematocrit tube, but preferably two, will be filled with the residual whole blood and then centrifuged.
- 11.6.2 The hematocrit will be measured from only one tube; the second tube will be collected as a backup in case the first tube is not measurable (i.e., tube spun out, broken tube, clay seal compromised, etc.). Additional details regarding hematocrit measurements are found in Appendix D.

11.7 Testing Schematic

Table 2. Sample Testing Schematic

Step	Test/action	Description		
1	Sample prep	 Ensure collection of residual neonatal sample in collection tube containing anticogulant (lithium/heparin). Confirm sufficient blood volume to perform all testing procedures. If so, then aliquot up to 50 uL into microtube and cover. 		
2	Testing prep	Assign one CONTOUR NEXT meter and one CONTOUR PLUS ELITE meter to the patient sample. Follow the strip lot randomization (red, green, blue) and get the test strip bottle for the respective meter. Get a piece of parafilm. For steps 3 and 4, follow meter test order per randomization schedule.		
3	Meter Test 1	 Put a test strip into each meter. Immediately place 1 drop of blood on the parafilm and test with both meters. Record results. In case of error, may repeat 2 more times with a new blood drop. Record time of successful meter tests. 		
4	Meter Test 2	■ Replace test strips, and place new blood drop on parafilm to repeat Step 3 for duplicate testing.		
5	Hematocrit	 Using the blood from the same collection tube, fill up to 2 hematocrit tubes. Perform hematocrit measurement, and record results. 		
6	Centrifugation	■ Centrifuge blood, and record start time. (The centrifugation start time must be within 10 min of meter tests).		
7	Laboratory tests*	 Perform blood glucose testing of plasma sample on laboratory analyzer (Cobas) in duplicate. Record results. 		

^{*} Pre-study and on-study serum control testing on Cobas: See 11.8 and Appendix C.

11.8 Accuracy and Precision of Cobas 6000

Performance of the Cobas 6000 will be tracked by two methods. The primary method will be the instrument QC check procedure regularly applied by the clinical site. In addition, serum controls will be provided by Ascensia for internal research purposes only, and will not impact the study data or data collection. See Appendix C for further details.

11.9 Bilirubin Data

Bilirubin data will be collected to assess potential interference with elevated bilirubin levels occurring in neonates. In cases where the prescribed test for the sample is a bilirubin analysis, the results of this test will be recorded as part of the study data from the hospital records.

No bilirubin test will be performed on study samples just for the purpose of this study. Thus, not all study samples may have bilirubin data.

11.10 Temperature and Humidity Logs

• The study staff will measure the temperature/humidity in the meter testing area once during the day that meter testing occurs and record the results on the appropriate log form.

• Study staff will maintain a temperature log for the storage of investigational materials including the meters, test strips, controls, and serum controls.

12.0 Monitoring Plan

- **12.1** A monitoring plan will be completed by the Study Manager/designee prior to the study.
- **12.2** The study manager or designee will conduct the SIV. The frequency of the number of monitoring visits by sponsor personnel or designee(s) will be based on the monitoring plan and will include at least 1-3 monitoring visits and a close-out visit.
- **12.3** Sponsor representatives may observe some study testing as part of study monitoring. This will be done under supervision of the Investigator.
- **12.4** Sponsor representatives will maintain subject confidentiality, and will not interfere with the rights of human subjects or safety, or bias study conduct.

13.0 Statistical Plan

13.1 Sample Size

- 13.1.1 The sample size requirement is based on the primary objective, section 7.0.
- 13.1.2 There will be a minimum of N = 120 study samples entered into the study. The meter results will be taken in duplicate, so that the total sample size of meter results will be at least 2*120 = 240.
- 13.1.3 With a sample size of n = 240 results, there is approximately a 95% chance that at least 228 of those results (95% of 240) will be "accurate" (errors within either ± 12 mg/dL (± 0.67 mmol/L) when the comparator result is < 100 mg/dL (5.55 mmol/L), or $\pm 12.5\%$ when the comparator result is ≥ 100 mg/dL (5.55 mmol/L) if the evaluation (meter) system has a 96.77% chance of yielding an "accurate" result.
- 13.1.4 Conversely, there is about a 95% chance of obtaining fewer than 228 "accurate" results if the system only has an approximately 92.03% chance of yielding an accurate result.
- 13.1.5 Note that each glucose result obtained with the evaluation devices will be considered either 'accurate' or 'not accurate', where accuracy depends on the particular test criterion as described in section 7.0 of this protocol.

Protocol /CIP: GCA-PRO-2021-003-01 - Amendment 1 Version: 14Oct2022

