7.0 Objectives and Hypotheses

Version: 140ct2022

The primary objective of the study is to evaluate the performance of CONTOUR NEXT and CONTOUR PLUS ELITE BGMSs with residual heel-stick capillary blood samples from neonates, i.e. babies who are less than 28 days old. The performance of the BGMS will be analyzed according to the following objectives:

- 7.1 **Primary Objective**: The accuracy criteria below are taken from CLSI. *Point-of-Care Blood* Glucose Testing in Acute and Chronic Care Facilities; Approved Guideline – Third Edition. CLSI document POCT12-A3. Wayne, PA: Clinical and Laboratory Standards Institute; 2013.
 - At least 95% of all blood glucose results shall fall within ±12.5% of reference values 7.1.1 (laboratory method) for glucose concentration ≥100 mg/dL (5.55 mmol/L) and within $\pm 12 \text{ mg/dL}$ ($\pm 0.67 \text{ mmol/L}$) at glucose concentrations < 100 mg/dL (5.55) mmol/L).
 - Note: Satisfying Criterion 7.1.1 would also satisfy the ISO 15917:2013 criteria of obtaining the $\pm 15\%$ of reference values (laboratory method) for glucose concentration $\geq 100 \text{ mg/dL}$ (5.55 mmol/L) and within $\pm 15 \text{ mg/dL}$ ($\pm 0.83 \text{ mmol/L}$) at glucose concentrations <100 mg/dL (5.55 mmol/L).
 - 7.1.2 At least 98% of values shall be within $\pm 20\%$ of reference values (laboratory method) for glucose concentration \geq 75 mg/dL (4.16 mmol/L) and within \pm 15 mg/dL (\pm 0.83 mmol/L) at glucose concentrations < 75 mg/dL (4.16 mmol/L).

Other Objectives: 7.2

- Evaluate the performance of both BGMSs for neonates who are <24 hours old. Compute differences between BGMS and laboratory blood glucose measurements and plot them against hematocrit results.
- Evaluate the performance of both BGMSs with blood samples from babies in the NICU.
- Compute differences between BGMS and laboratory blood glucose measurements and plot them against bilirubin results, for those subjects where bilirubin measurements were recorded (when available).

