13.5 Accuracy Analyses

13.5.1 Two sets of metrics will be calculated:

Relative (Percent) Difference (RD) for reference result \geq threshold glucose:

$$RD = \frac{M-C}{C} 100\%$$

where: M = strip/meter result and C = comparator or reference method result.

Difference (D) for reference result < threshold glucose:

$$D = M - C$$

Protocol /CIP: GCA-PRO-2021-003-01 - Amendment 1 Version: 14Oct2022

13.5.2 Primary objective:

The threshold glucose value is 100 mg/dL (5.55 mmol/L). Accuracy will be assessed using the CLSI. *Point-of-Care Blood Glucose Testing in Acute and Chronic Care Facilities; Approved Guideline – Third Edition*. CLSI document POCT12-A3. Wayne, PA: Clinical and Laboratory Standards Institute; 2013.

i.e., D within $\pm 12 \text{ mg/dL} (\pm 0.67 \text{ mmol/L})$ for comparator result < 100 mg/dL (5.55 mmol/L) and RD within $\pm 12.5\%$ for comparator result $\ge 100 \text{ mg/dL} (5.55 \text{ mmol/L})$.

For RD, the percent of results within $\pm 5\%$, $\pm 10\%$, $\pm 12.5\%$, $\pm 15\%$ and $\pm 20\%$ will be computed.

For D, the percent less than or equal to ± 5 mg/dL (± 0.28 mmol/L), ± 10 mg/dL (± 0.56 mmol/L), ± 12.0 mg/dL (± 0.67 mmol/L), ± 15 mg/dL (± 0.83 mmol/L), and ± 20 mg/dL (± 1.11 mmol/L) will be computed.

The *RD* and *D* distribution tables will be constructed using a threshold of 100 mg/dL(5.55 mmol/L).

As discussed in section 13.1 (Sample Size), with n = 240, the critical number (minimum) of accurate results is 228, which yields approximately 95% chance of satisfying the criterion if the actual probability that any result will be accurate is at least 96.77%. Symbolically, this criterion is equivalent to testing the hypothesis:

 $H_0: Prob\{accurate\} < 96.77\%$ versus the alternative:

 $H_1: Prob{accurate} \ge 96.77\%$

This test has a power of about 95%, with n =240, to reject H_0 if the actual probability of obtaining an accurate result is 96.77%. Conversely, there is about a 95% chance that the null will NOT be rejected if the actual probability that a result with the evaluation device would satisfy this definition of accuracy is only about 92.03%.

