13.5.3 The second part of the primary objective

The second part of the primary objective states that at least 98% of the n = 240 results must fall within ± 15 mg/dL(± 0.83 mmol/L) of the comparator result (comparator < 75 mg/dL/4.16 mmol/L)) or $\pm 20\%$ of the comparator result (comparator ≥ 75 mg/dL/4.16 mmol/L). Thus, with n = 240, there must be at least 236 BGMS results satisfying this requirement. This is equivalent to testing the hypotheses:

*H*₀: $Prob\{accurate\} < 98.33\%$ versus the alternative:

 H_1 : $Prob{accurate} \ge 98.33\%$

There is approximately a 95% chance of rejecting H_0 in favor of H_1 if the actual probability that a meter measurement would satisfy the ± 15 mg/dL or 20% is 98.33%. Conversely, there is about a 95% chance that the null will NOT be rejected if the actual probability that a result with the evaluation device would satisfy this definition of accuracy is only about 96.23%. It is possible

Protocol /CIP: GCA-PRO-2021-003-01 - Amendment 1 Ascensia Diabetes Care CONFIDENTIAL

that the sample size after the study is completed may not be exactly 240. The critical values will be approximately 95% or 98% of results (first and second parts of primary objective, respectively), and the associated hypotheses will be adjusted to reflect the change while maintaining no more than a 95% chance of rejecting the null hypotheses.

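### Section 13.1 gives a passing chance for only one of the two parts of the primary objective, and 13.5.3 misstates the other: at 98.33% it is about 63%, not about 95%, so the chance of meeting both is about 62%

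*Combined protocol and SAP*

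**What the plan says.** Section 7.1 lists two accuracy criteria under one primary objective.

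- **7.1.1:** at least 95% of results within ±12 mg/dL of the reference below 100 mg/dL, or within ±12.5% from 100 mg/dL up.
- **7.1.2:** "At least 98% of values shall be within" ±15 mg/dL below 75 mg/dL, or ±20% from 75 mg/dL up.

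On the sample size, 13.1.1 states: "The sample size requirement is based on the primary objective, section 7.0". The operating figures that follow concern 7.1.1 alone. Section 13.1.3 says "With a sample size of n = 240 results, there is approximately a 95% chance that at least 228 of those results" will be accurate if the "system has a 96.77% chance of yielding an" accurate result. Section 13.1.4 gives the lower point: about a 95% chance of fewer than 228 "if the system only has an approximately 92.03% chance of yielding an accurate result". Section 13.5.2 repeats this: "the critical number (minimum) of accurate results is 228, which yields approximately 95% chance of satisfying the criterion".

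Criterion 7.1.2 is handled in 13.5.3: "The second part of the primary objective states that at least 98% of the n = 240 results must fall within" its limits. The cut-off is then set: "Thus, with n = 240, there must be at least 236 BGMS results satisfying this requirement". That section claims roughly a 95% chance of passing at a true probability of 98.33%, and roughly a 95% chance of not passing at 96.23%.

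Neither section gives a chance of meeting both parts. Section 8.2 sets 240 results for each BGMS, so all of these figures are per BGMS.

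**The concern.** A sample size said to rest on the primary objective should come with operating figures for the whole objective. Section 13.1 supplies them for one part. A reader who wants the rest must go to 13.5.3, where the chance of passing is also given as about 95%. Taken together, the two sections suggest that a meter at the stated design values is very likely to succeed. If the second figure is wrong, the sponsor is planning on a chance of success that the design does not deliver at those values, and the accuracy a meter needs in order to pass 7.1.2 reliably is understated.

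**Working it through.** **Inputs.** n = 240 results per BGMS (8.2, 13.1.2). First part: pass at 228 or more, design value 96.77%, lower point 92.03% (13.1.3, 13.1.4). Second part: pass at 236 or more, design value 98.33%, lower point 96.23% (13.5.3). Results are treated as independent, as the plan's figures imply.

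**Step 1: each rule alone.** With X ~ Binomial(240, p):

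| Rule | True p | Plan's chance of passing | Recomputed |
|---|---|---|---|
| X ≥ 228 | 96.77% | about 95% | 95.0% |
| X ≥ 228 | 92.03% | about 5% | 5.0% |
| X ≥ 236 | 96.23% | about 5% | 5.0% |
| X ≥ 236 | 98.33% | about 95% | **62.7%** |

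Three of the four figures reproduce; the last does not. The value 98.33% is simply 236/240, the pass fraction itself, and a meter whose true accuracy equals the pass fraction cannot pass 95% of the time. A slip of one in the cut-off does not explain it: P(X ≥ 235) at 98.33% is 78.5%. Solving P(X ≥ 236) = 0.95 gives p = 99.18% (0.99176).

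**Step 2: the two parts are nested.** Compare the limits by reference glucose C:

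- C below 75 mg/dL: ±12 against ±15 mg/dL.
- C from 75 to below 100 mg/dL: ±12 mg/dL against ±20% of C, which is at least 0.20 × 75 = 15 mg/dL.
- C of 100 mg/dL or more: ±12.5% against ±20%.

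In every band a result that misses 7.1.2 also misses 7.1.1, so the joint chance can be computed exactly.

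**Step 3: chance of meeting both.** Let p1 and p2 be the true probabilities for the two parts, and K ~ Binomial(240, 1 − p2) the number of 7.1.2 misses. Given K = k, the results that miss 7.1.1 only are Binomial(240 − k, q), with q = (p2 − p1)/p2. At most 4 misses of 7.1.2 and at most 12 of 7.1.1 are allowed, so

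P(both) = Σ (k = 0 to 4) P(K = k) × P(7.1.1-only misses ≤ 12 − k).

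For p1 = 0.9677 and p2 = 0.9833, q = 0.0156/0.9833 = 0.01586:

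| k | P(K = k) | P(7.1.1-only misses ≤ 12 − k) | Product |
|---|---|---|---|
| 0 | 0.0176 | 0.9999 | 0.0176 |
| 1 | 0.0716 | 0.9995 | 0.0716 |
| 2 | 0.1453 | 0.9983 | 0.1451 |
| 3 | 0.1958 | 0.9950 | 0.1948 |
| 4 | 0.1970 | 0.9861 | 0.1943 |

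The sum is 0.623. Nesting is not critical to this: whatever the dependence between the parts, the joint chance must lie between 0.950 + 0.627 − 1 = 0.578 (from unrounded inputs) and 0.627.

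The same sum with p2 = 0.99176, where each rule alone has 95%, gives 0.914.

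**Step 4: where the shortfall comes from.** At 98.33% the second rule alone has 62.7%, and also requiring the first takes off 62.7 − 62.3 = 0.4 points. Where each rule truly has 95%, requiring both takes off 95.0 − 91.4 = 3.6 points.

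**Step 5: correlated duplicates.** The documents give no correlation between the duplicates. Simulation over an assumed range of 0 to 1 puts the joint chance between about 61% and 66%. The first part alone falls to about 89–91% at the assumed values of 0.5 and above.

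**The case against.** Four points can be made for the plan.

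1. *Section 13.1.3 is open about its scope.* It names the ±12 mg/dL and ±12.5% limits in the same sentence as the 95%, and 13.1.5 says that accuracy depends on the criterion in question. This stands: 13.1 is incomplete, but it does not present its 95% as covering both parts.

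2. *The second part does have operating figures, in 13.5.3.* True, but the chance given at its design value is wrong. A reader might blame the 62% on the lack of a joint calculation; Step 4 shows that it is nearly all the 13.5.3 error.

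3. *The plan never says that one meter has both 96.77% and 98.33%.* Also true: they are separate design values, paired here because they are the only ones given. If errors were normal with no bias and 96.77% fell within the first limits, the second probability would be 99.25% below 75 mg/dL and 99.94% from 100 mg/dL up, and the joint chance about 92.5% to 95.0%. That error model is an assumption, and heavier tails would lower the figures. So 62% describes the plan's stated values and does not forecast how these meters will perform.

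4. *Both parts are plainly required.* A reader might infer, since no sentence joins the two criteria, that meeting either could count as success and that false passes could then exceed 5%. The documents do not support this. Section 7.1 states each criterion as an obligation, and 13.5.3 calls 7.1.2 the second part of the objective and a requirement. No section proposes an either-suffices rule. With both required, the false-pass chance at 92.03% and 96.23% is 1.8%.

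**Conclusion.** The point holds as an incomplete operating statement in 13.1 combined with a wrong figure in 13.5.3. At 98.33% the chance of passing 7.1.2 is 62.7%; the 95% point is about 99.18%. For one BGMS, the chance of meeting the whole primary objective is about 62% at 96.77% and 98.33%, and about 91% at 96.77% and 99.18%. These figures assume 240 independent results and limits nested as in 7.1; plausible correlation between duplicates does not change the conclusion. The missing sentence requiring both parts is a matter of clarity, and no error-rate problem follows from it.

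**What to change.** Keep 120 samples and change wording only.

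1. In 13.5.3, either restate the chance of passing at 98.33% as about 63%, or restate the 95% point as about 99.18%. The hypotheses there are also written with 98.33% and should agree with the choice made. This has to accompany item 2; otherwise 13.1 and 13.5.3 would contradict each other, since a joint chance cannot exceed that of either part.
2. In 13.1, add the chance that one BGMS meets both parts next to the 7.1.1 figure: about 62% at 96.77% and 98.33%, and about 91% at 96.77% and 99.18%. State the independence assumption.
3. In 7.1 and 13.5, say explicitly that each BGMS meets the primary objective only if it meets both parts. Requiring both cannot raise the false-pass chance above that of either rule alone, so no alpha adjustment is needed.

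The cost is editing three sections and accepting a less favourable stated chance of success. No samples or procedures are added.

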13.2 Blood Glucose Measurements

Data analysis follows analyses and presentations described in CLSI. *Point-of-Care Blood Glucose Testing in Acute and Chronic Care Facilities; Approved Guideline – Third Edition*. CLSI document POCT12-A3. Wayne, PA: Clinical and Laboratory Standards Institute; 2013.

The unit conversion formula for blood glucose is the following:

Xmmol/L = Ymg/dL / 18.016

13.3 Bland-Altman Plots

Modified Bland-Altman plots (the difference between each evaluation device results and reference results plotted against reference results) will be constructed.

13.4 Weighted Least Squares Regression

Weighted least squares regressions of meter results against comparator results will be performed. If *M* represents the meter result, and *C* the comparator result, the linear model can be expressed as:

$$M = \beta_0 + \beta_1 C + \varepsilon$$
$$\varepsilon \sim N(0, cv * C)$$

The parameter *cv* is the coefficient of variation, which is assumed to be constant across the glucose range. The weighting function will be:

$$w = C^{-2}$$

This weighting function is used to account for the constant cv nature of glucose measurement (Draper and Smith, 1998).

13.5 Accuracy Analyses

13.5.1 Two sets of metrics will be calculated:

Relative (Percent) Difference (RD) for reference result \geq threshold glucose:

$$RD = \frac{M-C}{C} 100\%$$

where: M = strip/meter result and C = comparator or reference method result.

Difference (D) for reference result < threshold glucose:

$$D = M - C$$

Protocol /CIP: GCA-PRO-2021-003-01 - Amendment 1 Version: 14Oct2022

13.5.2 Primary objective:

The threshold glucose value is 100 mg/dL (5.55 mmol/L). Accuracy will be assessed using the CLSI. *Point-of-Care Blood Glucose Testing in Acute and Chronic Care Facilities; Approved Guideline – Third Edition*. CLSI document POCT12-A3. Wayne, PA: Clinical and Laboratory Standards Institute; 2013.

i.e., D within $\pm 12 \text{ mg/dL} (\pm 0.67 \text{ mmol/L})$ for comparator result < 100 mg/dL (5.55 mmol/L) and RD within $\pm 12.5\%$ for comparator result $\ge 100 \text{ mg/dL} (5.55 \text{ mmol/L})$.

For RD, the percent of results within $\pm 5\%$, $\pm 10\%$, $\pm 12.5\%$, $\pm 15\%$ and $\pm 20\%$ will be computed.

For D, the percent less than or equal to ± 5 mg/dL (± 0.28 mmol/L), ± 10 mg/dL (± 0.56 mmol/L), ± 12.0 mg/dL (± 0.67 mmol/L), ± 15 mg/dL (± 0.83 mmol/L), and ± 20 mg/dL (± 1.11 mmol/L) will be computed.

The *RD* and *D* distribution tables will be constructed using a threshold of 100 mg/dL(5.55 mmol/L).

As discussed in section 13.1 (Sample Size), with n = 240, the critical number (minimum) of accurate results is 228, which yields approximately 95% chance of satisfying the criterion if the actual probability that any result will be accurate is at least 96.77%. Symbolically, this criterion is equivalent to testing the hypothesis:

 $H_0: Prob\{accurate\} < 96.77\%$ versus the alternative:

 $H_1: Prob{accurate} \ge 96.77\%$

This test has a power of about 95%, with n =240, to reject H_0 if the actual probability of obtaining an accurate result is 96.77%. Conversely, there is about a 95% chance that the null will NOT be rejected if the actual probability that a result with the evaluation device would satisfy this definition of accuracy is only about 92.03%.

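### The hypotheses attached to the 228/240 and 236/240 rules are not the ones those rules test, and the 95% chance claimed for criterion 2 at a true rate of 98.33% is 62.7%

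*Combined protocol and SAP*

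**What the plan says.** Section 7.1 sets two accuracy criteria on observed shares: at least 95% of results within the first limits, and at least 98% within the second. Section 13 turns these into counts out of 240 results per system.

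- **Criterion 1.** Section 13.1.3 says "With a sample size of n = 240 results, there is approximately a 95% chance that at least 228 of those results" will be accurate when the true rate is 96.77%. Section 13.1.4 gives about a 95% chance of falling short of 228 "if the system only has an approximately 92.03% chance of yielding an accurate result". Section 13.5.2 repeats that "the critical number (minimum) of accurate results is 228" and calls the rule equivalent to testing H0: p < 96.77% against H1: p ≥ 96.77%. It adds: "This test has a power of about 95%, with n =240, to reject H_0 if the actual probability of obtaining an accurate result" is 96.77%.
- **Criterion 2.** Section 13.5.3 requires at least 236 of 240 and equates this with testing H0: p < 98.33% against H1: p ≥ 98.33%. It says "There is approximately a 95% chance of rejecting H_0 in favor of H_1 if the actual probability" of meeting the limits is 98.33%, and that non-rejection has about a 95% chance at 96.23%.
- **Other sample sizes.** If n is not exactly 240, the cut-offs stay at approximately 95% or 98%, and the "associated hypotheses will be adjusted to reflect the change while maintaining no more than a 95% chance of rejecting the null hypotheses".

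Neither 13.1 nor 13.5 states an alpha level.

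**The concern.** A null hypothesis should describe performance that the rule rarely passes. Here the stated null for criterion 1 runs up to 96.77%, the rate at which the rule nearly always passes. A system just below 96.77% satisfies H0 and is still declared to have rejected it about 95% of the time.

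For criterion 2 the null boundary of 98.33% is simply 236/240, the pass mark expressed as a share. A system whose true rate equals the pass mark should clear it somewhat more than half the time, so a 95% chance is implausible on its face.

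Two things are at stake. A report that follows 13.5 could claim that p < 96.77% was rejected on an observed 95.0%, which overstates what the data show about accuracy in neonates. The sponsor is also planning on a 5% risk of failing criterion 2 at 98.33% when the risk is far larger.

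**Working it through.** **Inputs.** n = 240 and cut-off 228 (13.1.2, 13.1.3, 13.5.2); cut-off 236 (13.5.3); rates 96.77% and 92.03% (13.1.3, 13.1.4, 13.5.2); rates 98.33% and 96.23% (13.5.3). The 240 results are treated as independent, as the plan does.

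**Formula.** The chance of passing with cut-off c at true rate p is P(X ≥ c) = Σ (k = c to 240) C(240, k) p^k (1 − p)^(240 − k).

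**Step 1: the plan's four operating points.**

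| Rule | True rate | Plan | Exact binomial |
|---|---|---|---|
| ≥ 228 | 96.77% | about 95% pass | 0.9503 pass |
| ≥ 228 | 92.03% | about 95% fail | 1 − 0.0503 = 0.9497 fail |
| ≥ 236 | 96.23% | about 95% fail | 1 − 0.0502 = 0.9498 fail |
| ≥ 236 | 98.33% | about 95% pass | **0.6273 pass** |

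Three reproduce and one does not. For the fourth, passing means at most 4 inaccurate results when each has probability 0.0167. The terms for 0, 1, 2, 3 and 4 inaccurate results are 0.0176 + 0.0716 + 0.1453 + 0.1958 + 0.1970 = 0.6273. The chance of failing is therefore 37.3%, not 5%.

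**Step 2: does another reading rescue the 95%?** At 98.33%, a cut-off of 235 gives 0.785, 234 gives 0.890 and 233 gives 0.950. But 233/240 = 97.1%, which breaks the 98% rule. The normal approximation gives 0.498, or 0.598 with continuity correction; the Poisson gives 0.627. Keeping the cut-off at 236, the pass chance is 0.9509 at p = 99.18%. That is the criterion 2 counterpart of 96.77%.

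**Step 3: error rate of the tests as written.** Type I error is the largest pass chance over H0, and the pass chance rises with p, so it is approached at the boundary.

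- Criterion 1, H0: p < 96.77%: up to 0.9503. A 5% test of that null would need 237/240 (0.0475; 236 gives 0.1108).
- Criterion 2, H0: p < 98.33%: up to 0.6273. A 5% test would need 240/240 (0.0176; 239 gives 0.0892).

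**Step 4: the hypotheses that the rules do test at about 5%.** From Step 1, these are p ≤ 92.03% (0.0503) and p ≤ 96.23% (0.0502). The one-sided 95% Clopper-Pearson lower bounds at the cut-offs agree: 92.02% at 228/240 and 96.23% at 236/240. An observed 228/240 (95.0%) thus supports p > 92.0%, not p ≥ 96.77%.

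**Step 5: other n.** Rounding the 95% and 98% cut-offs up, as the plan does with 236 (0.98 × 240 = 235.2), the rates with a 5% pass chance are:

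| n | Cut-offs | Null values |
|---|---|---|
| 242 | 230 and 238 | 92.09% and 96.26% |
| 400 (200 samples in duplicate) | 380 and 392 | 92.82% and 96.42% |

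The null moves with n. A 95% ceiling on rejection does not determine it.

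**The case against.** The strongest reply is that the objective is an observed share. Section 7.1 decides pass or fail, and none of the cut-offs, the sample size or the data collection depends on how 13.5 labels its hypotheses. For criterion 1, sections 13.1 and 13.5.2 give both operating points correctly, so a careful reader knows how the 228/240 rule behaves. The plan does not expressly commit to reporting a p-value or a formal rejection. The values 92.03% and 96.23% are simply where the fixed cut-offs give about 5%, and the documents offer no clinical reason for them. The clause on other n may be only a slip of the pen.

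Much of this is true and limits the severity. It does not remove the point. Section 13.5 is the formal analysis of the primary objective and expressly equates the rules with these tests. The 95% at 98.33% is a wrong number under any labelling.

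A second objection stands as a condition on the fix. The 240 results are duplicates from 120 samples, so an alpha of about 5% holds only if the duplicates are independent. The documents give no concordance figure. At the opposite extreme, fully concordant duplicates (120 units, cut-offs 114 and 118), the pass chance is 14.9% at 92.03% and 16.6% at 96.23%. The lower bounds, taken as the 5% quantile of Beta(x, n − x + 1), fall to 90.4% and 94.8%. The criterion 2 pass chance at 98.33% becomes 67.6%, still far from 95%.

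**Conclusion.** The concern holds and should be fixed. The hypotheses in 13.5.2 and 13.5.3 are not those that the 228/240 and 236/240 rules test: as written, the type I error approaches 95.0% and 62.7%. The rules are tests at about 5% of p ≤ 92.03% and p ≤ 96.23%. Separately, the pass chance stated for criterion 2 at 98.33% overstates 62.7% as 95%. The clause on other n carries the inversion into an instruction for analysis.

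These figures are exact binomial and rest on the plan's own assumption of 240 independent results. The observed-share pass/fail decision does not change.

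**What to change.** - **Criterion 1 (13.5.2):** H0: p ≤ 92.03% against H1: p > 92.03%, one-sided alpha about 5%, power about 95% at 96.77%.
- **Criterion 2 (13.5.3):** H0: p ≤ 96.23% against H1: p > 96.23%, alpha about 5%, power about 63% at 98.33% and about 95% at 99.18%. Delete the 95% claim at 98.33%.
- **Other n:** keep the section 7.1 cut-offs by rounding 95% and 98% of n up, and recompute the null value for the achieved n. Replace the 95% ceiling with a pass chance of about 5% when p is at the null value.
- **Assumption:** say beside each alpha, power or bound that it treats duplicates as independent.
- **Useful addition:** report a one-sided lower confidence bound with each pass/fail result, preferably one that allows for the pairing.

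Dropping the formal hypotheses and giving only correct operating characteristics would also remove the error.

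The cost is wording in section 13.5; cut-offs, n and data collection stay as they are. The price is a less favourable formal claim (p > 92.0% and p > 96.2%) and a lower stated power for criterion 2 at 98.33%.
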